**b. Gene therapy**

- *N/A*

## **7. Risks and Discomforts**

**b. General**

rTMS, as delivered under this protocol, involves more than minimal risk to participants. The behavioral tasks, neuroimaging procedures, and screening procedures are minimal risks to the participant.

**c. Study Procedures**

i. Behavioral measures

There are no major risks associated with these memory tests other than frustration or embarrassment associated with the participants' performance.

ii. MRI

People are at risk for injury from the MRI magnet if they have pacemakers or other implanted electrical devices, brain stimulators, some types of dental implants, aneurysm clips (metal clips on the wall of a large artery), metallic prostheses (including metal pins and rods, heart valves, and cochlear implants), permanent eyeliner, implanted delivery pump, or shrapnel fragments. Welders and metal workers are also at risk for injury because of possible small metal fragments in the eye of which they may be unaware. People with fear of confined spaces may become anxious during an MRI. Those with back problems may have back pain or discomfort from lying in the scanner. The noise from the scanner is loud enough to damage hearing, especially in people who already have hearing loss. Participants will be fitted with ear plugs. There are no known long-term risks of MRI scanning.

iii. TMS

There is a small possibility of a seizure during TMS. TMS has been found to produce hearing loss in experimental animals, caused by the click produced by the stimulating coil. However, no evidence of chronic hearing loss when hearing protection was used, in several normal participants who had been extensively studied with TMS was found, nor transient changes in several participants tested before, and immediately after stimulation (Pascual-Leone et al., 1992) and more recent has found no increase in auditory threshold from TMS (Janicak et al., 2008; Levkovitz et al., 2007). All of our participants will wear earplugs to reduce the risk of cochlear damage. Other than this, TMS does not appear to pose any hazard to the brain beyond that of electric stimulation, which has been in clinical use for decades. The World Health Organization task group and the Food and Drug Administration concluded that brief exposure to static magnetic fields up to 2 Tesla have no adverse effects on human health ).

**d. Procedures to Minimize Risk**

i. Behavioral measures

To minimize the risk associated with frustration or embarrassment, the researcher will maintain a positive attitude and observe the participants' behavior to determine if they are overly frustrated. Breaks will be at subject's discretion.

ii. MRI

To mitigate the risk of damage associated with exposure to a powerful magnet, all magnetic objects (for example, watches, coins, jewelry, and credit cards) must be removed before entering the MRI scan room. In addition, participants will be screened for metal implants such as pacemakers or other implanted electrical devices, brain stimulators, some types of dental implants, aneurysm clips (metal clips on the wall of a large artery), metallic prostheses (including metal pins and rods, heart valves, and cochlear implants), permanent eyeliner, tattoos posing MRI risk, implanted delivery pump, or shrapnel fragments.

To minimize the risk of hearing damage, participants will be given earplugs or noise reducing headphones. To confirm that our female participants are not pregnant, thus removing any unknown risks of MRI on a fetus, women of childbearing potential will have a urine pregnancy test within 24 hours of participation in the fMRI experiment. Female participants will not be allowed to participate if the test is positive. There are no risks of pregnancy testing.

iii. TMS

Study staff will be trained in rTMS administration, rTMS safety, and the measurement of the TMS-evoked potentials by [name]. Study staff will be trained to recognize and respond to signs of seizure and syncope. For each session, at least two rTMS-trained personnel will be in the laboratory. A licensed independent practitioner (LIP), a physician or nurse practitioner trained in rTMS, will be in house, specifically aware of the session, and reachable by phone for all TMS sessions. The TMS laboratory is in a clinic area with nursing and code team support. Each room has oxygen, suction, and an emergency call button. If a participant has a significant event, such as a seizure, the hospital emergency system (Code Blue) will be activated and treatment will be initiated as required.

Study staff will monitor individuals during participation and participants will be encouraged to tell experimenters of any discomfort. At each session, participants will be asked whether stimulation was (1) tolerable, (2) tolerable with some discomfort, or (3) intolerable. If the participant responds that stimulation is intolerable, the participant will be withdrawn from the experiment. Any participant exhibiting distress or who wishes to stop the experiment for any reason will be allowed to stop. Nonprescription drugs may be used to alleviate headache or pain discomfort.

Syncope will be treated safely by immediately placing the participant in a lying position with legs elevated. Should any participant become faint, the LIP covering the study will be called immediately.

Although no long-term deleterious effects of rTMS cognition have been reported, we will monitor cognition with the NIH Toolbox. This is a standardized assessment with age-adjusted normative values. An investigator will review NIH Toolbox results for each participant at the post-stimulation and 2-week follow-up assessments. If a participant experiences a significant drop from baseline, the IMM will be informed and the test(s) repeated in a few days. If the deficit persists, the participant will be withdrawn from the study and referred for clinical neuropsychological evaluation. If, in the judgment of [name] or IMM, a study procedure is causing frequent unexpected or adverse events of any kind, the study will be suspended until a review can be undertaken in consultation with the IRB. Depending on the outcome, the protocol may be amended, and/or specific language added to the protocol and documents to reflect the altered risk.

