## 4. Study Design and Methods

### a. Study overview

This protocol will include four experiments, each using rTMS and MRI, in a between-subjects design (Table 1). Experiments 1 and 3 will use PPC rTMS. Experiments 2 and 4 will use M1 stimulation.

	Active Stimulation Type	Active Stimulation Site	Targeted Network
Experiment 1	Facilitatory (20-Hz)	PPC	Hippocampal
Experiment 2	Facilitatory (20-Hz)	M1	Striatal
Experiment 3	Inhibitory (cTBS or 1-Hz)	PPC	Hippocampal
Experiment 4	Inhibitory (cTBS or 1-Hz)	M1	Striatal

Table 1. Experiment Details. PPC = Posterior Parietal Cortex, M1 = Motor Cortex.

Table 2 shows the timeline of each experiment. Each study will include FC and memory testing at baseline, 24-hours after, and two weeks after three days of rTMS. The number of days of rTMS is based on pilot data where three days of stimulation produces significant enhancement of rsFC in the hippocampal network in five out of six individuals tested. Each participant will make a maximum of 6 visits to the lab (not including screening), for a maximum time commitment of 14 hours. The 24-hour follow-up will occur between 12 and 48 hours after the last stimulation session, and the 2-week follow-up will occur 14-21 days after baseline measurements. Scanning will occur in the NIH NMRF. All visits will be outpatient.

	Baseline Day	rTMS Sessions	Post Stimulation Day	2-week follow-up
Group 1	Baseline FC and Memory	Active Stimulation 3-sessions	FC and Memory Testing	FC and Memory Testing
Group 2	Baseline FC and Memory	Vertex Stimulation 3-sessions	FC and Memory Testing	FC and Memory Testing

Table 2. Timeline of each experiment.

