#### v. Cognitive Battery

The purpose of the battery is to detect effects on other memory processes other than those targeted in the study, characterize participants cognitive abilities at baseline, and to monitor for unexpected deleterious effects of stimulation. The data will be treated as exploratory. Some tasks will only be included at baseline (indicated below). These tests will not be given inside of the scanner. The battery includes the following tests:

- 1) Flanker Inhibitory Control and Attention Test (executive function and attention) - Participants respond to the direction of a target arrow while inhibiting attention to arrows flanking the target arrow (~3 minutes). This test will only be given at baseline.
- 2) Dimensional Change Card Sort Test (executive function and set-shifting) – Participants must match pictures based on one of two rules. These rules are transposed and participants' set-shifting abilities are measured by their accuracy and reaction time (~4 minutes). This test will only be given at baseline.
- 3) List Sorting Working Memory Test (for working memory) – Participants are given two lists of items (e.g. animals and foods) and are asked to list the items in size order. The task requires the

participant to concurrently remember the items while sorting (< 10 minutes). This test will only be given at baseline.

- 4) Picture Sequence Memory Test (for story sequence memory) – Participants are given a list of objects and must remember the order of these objects in relation to each other. For example, if object A is listed in position X, the participant must recall what object is in position X+1 (~7 minutes).
- 5) Oral Reading Recognition Test (for language) – The participant is asked to read individual words and the researcher records whether the word is read correctly (~3 minutes). This test will only be given at baseline.
- 6) The Picture Vocabulary Test (for language) – Participants are aurally presented with a word and must match that word with one of four pictures that best represents the meaning of the word. The number of correct responses is recorded (~4 minutes). This test will only be given at baseline.
- 7) Pattern Comparison Processing Speed Test (for processing speed) – Participants are presented with two pictures and must determine whether they are the same or different. The number of correct responses in 90 seconds is recorded (~3 minutes). This test will only be given at baseline.

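### An answer of 'intolerable' ends the whole study for that participant, so some stimulated volunteers leave with no scheduled cognitive check (minor)

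*Combined protocol and SAP*

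**What the plan says.** Section 7.d.iii (Procedures to Minimize Risk, TMS) sets the rule in two sentences: "At each session, participants will be asked whether stimulation was (1) tolerable, (2) tolerable with some discomfort, or (3) intolerable", followed by "If the participant responds that stimulation is intolerable, the participant will be withdrawn from the experiment". Withdrawal is mandatory, applies at any session including the third, and covers the experiment as a whole.

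The same section describes the cognitive safety check: "An investigator will review NIH Toolbox results for each participant at the post-stimulation and 2-week follow-up assessments". A significant drop from baseline is reported to the medical monitor and retested, and a persistent deficit leads to referral. Section 4.d.v gives the battery several purposes, one of them "to monitor for unexpected deleterious effects of stimulation".

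The timing is in Section 4.a: "Each study will include FC and memory testing at baseline, 24-hours after, and two weeks after three days of rTMS". The first follow-up has this window: "The 24-hour follow-up will occur between 12 and 48 hours after the last stimulation session". The second is counted from a different starting point: "the 2-week follow-up will occur 14-21 days after baseline measurements".

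Other relevant rules:

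- Section 9.a: the primary outcome is the pre-to-post change in functional connectivity (FC) within the targeted network.
- Section 3.a: withdrawn participants are replaced.
- Section 4.b.i: missed visits are rescheduled with a new baseline, and a participant who misses only the two-week visit counts as complete.
- Section 8: data already collected from anyone who finished the first session are retained for analysis.
- Section 4.e: care is limited to acute treatment of adverse events.

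**The concern.** The rule treats stopping stimulation and leaving the study as one step. The first protects the participant. The second also removes the only scheduled occasions on which a cognitive change after stimulation would be looked for, in people who have been stimulated and tolerated it badly.

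There is a smaller consequence for the data. A participant who completes the third session and then answers 'intolerable' has received the planned exposure and is one visit short of the primary outcome. Under the rule that visit does not take place, and a new volunteer is recruited for up to six visits.

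**Working it through.** **1. The texts side by side**

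- Withdrawal can be triggered at session 1, 2 or 3 (Section 7.d.iii).
- Both post-stimulation assessments come after the three days of rTMS (Section 4.a). Every withdrawal under this rule therefore falls before the first of them.
- No section describes an early-stop visit. Section 4.b.i covers missed visits, not withdrawal. Section 8 retains what was collected, which for these participants is baseline only.
- Section 8 does not itself require the rule. Its stopping reasons are discretionary for the researcher or tied to the participant being unwilling to continue.

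**2. The plan's own figure**

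Sections 3.a and 10.b give 104 participants, about 15% attrition and a ceiling of 122. Check: 104 / (1 − 0.15) = 122.35, which agrees with 122. Places above target: 122 − 104 = 18. These cover screening failures as well as all dropout.

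**3. How many people**

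The rate of 'intolerable' answers is not given, so two assumed ranges are shown.

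| Assumed share of the 18 places | People, N | Per group (N / 8) |
|---|---|---|
| 25% | 4.5 | 0.56 |
| 50% | 9 | 1.1 |
| 100% (extreme bound) | 18 | 2.25 |

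| Assumed rate p per participant | Expected among 104 (104p) | Chance of at least one in a group of 13, 1 − (1 − p)^13 |
|---|---|---|
| 2% | 2.1 | 23% |
| 5% | 5.2 | 49% |
| 10% | 10.4 | 75% |
| 15% | 15.6 | 88% |

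**4. What a cognitive-only visit involves**

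Section 4.d.v marks items 1, 2, 3, 5, 6 and 7 as baseline-only. The repeated items are 4, 8, 9, 10, 11 and 12: 7 + 5 + 2 + 5 + 3 + 20 = 42 minutes, with the figure task's 20-minute delay filled by other tests. Of this, 23 minutes (items 11 and 12) are self-report.

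Payment under Section 21, if its rates apply: $20 for the first hour + $20 for behavioral tasks = $40. At most two visits per person gives 2N = 9, 18 or 36 visits, or $360, $720 or $1,440 if all are cognitive-only.

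**5. What a visit with MRI involves**

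A scan of up to 2 hours, the 42-minute battery and a resting-state questionnaire of under 8 minutes come to under 2 h 50 min. If part hours round up to three hours, payment is $20 + $10 + $10 for time, $40 for fMRI and $20 for tasks = $100, plus $10 if a pregnancy test is needed. Scanner time is extra.

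**6. Offset from avoided replacements**

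Let s be the share of stops that follow a completed third session (unknown, 0 to 1). Each avoids a replacement of at most six visits (Section 4.a), so net added visits = 2N − 6sN.

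- s = 0: 9, 18 or 36 added.
- s = 1/3: zero, with 1.5, 3 or 6 people keeping a full-course outcome.
- s = 1: 18, 36 or 72 saved.

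The offset requires MRI visits, so it cannot be set against the $40 figure.

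**The case against.** The rule sits among the risk-minimizing procedures and concerns healthy volunteers with nothing to gain from treatment. Ending participation spares a distressed person a request to return. That argues for stopping stimulation and for making further visits voluntary. It does not argue against offering them, so it does not remove the point.

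Several stronger readings are tempting, and here the objection stands:

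- *A reader might infer that a safety promise to every participant is broken.* The sentence on Toolbox review can equally describe what happens to results from assessments that take place. It does not clearly commit to assessing everyone ever stimulated, and no text forbids follow-up. What remains is that none is scheduled.
- *A reader might infer that any third-session answer means a full course was given and its data discarded.* Participants may stop at any time, so an intolerable session may have been cut short. The outcome data are not discarded; they are never collected. The point is limited to completed third sessions.
- *A reader might infer a biased FC comparison.* The control group receives vertex stimulation at the same settings, so stops can occur in both groups, and nothing in the documents indicates an imbalance or a link with outcome.
- *A reader might infer that early stoppers face higher cognitive risk.* The documents do not show this, and Section 7.d.iii says no long-term harm to cognition from rTMS has been reported.

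The check that is lost is also narrow. Half the battery is baseline-only, and the protocol does not say which of the twelve items belong to the NIH Toolbox, so the formal review may cover fewer than six. Adverse-event evaluation and acute care continue regardless. Replacement restores the sample size.

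**Conclusion.** The point holds in limited form. A stated rule withdraws stimulated participants before the only scheduled cognitive follow-up, and after a completed third session it also forgoes a primary outcome that one visit would supply. Stopping stimulation alone would give the same protection without either loss.

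The size is small and uncertain. The counts rest entirely on assumed intolerability rates, and the upper figure of 18 people would require every spare place to go to this one cause. Severity: optional, minor.

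**What to change.** Amend Sections 7.d.iii and 8, with matching consent wording:

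- An 'intolerable' answer stops rTMS at once but does not by itself end participation. Anyone who wants no further visits leaves as now.
- Willing participants are offered the existing assessments: 12 to 48 hours after the last session received, and 14 to 21 days after baseline. The minimum content is the six repeated battery items.
- Those who completed all three full sessions are also offered the post-stimulation MRI and both Weather Prediction Tasks, stay in the full-course analysis and are not replaced.
- Partial-course participants are replaced as now, and the full-course comparison remains primary.
- Stops for intolerability are reported by group and session.

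The cost is a short amendment and up to two voluntary visits per person who stops, priced in the working above. Avoided replacements offset part of this, by an amount that depends on how many stops follow a completed third session. The analysis changes only by retaining those participants.

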#### TMS Training

In accordance with safety guidelines, the TMS operator is a TMS-trained technician who operates under the supervision of the PI and/or Medically Responsible Investigator. Examples of TMS operators include medical assistants, technicians with relevant experience, psychologists, physicists, physiotherapists, engineers, physician assistants, nurses, nurse practitioners, and physicians.

Persons operating TMS equipment will have been certified by a NINDS laboratory in safe application of TMS.

Standard training procedures used include training in TMS device operation, supervised repeated practice in TMS procedures, and testing for inter-rater reliability in motor threshold determination. To be credentialed as a TMS technician, an individual must have passed the following criteria (as assessed by a designated BNU TMS instructor):

- 1) Training in TMS device operation
- 2) Supervised administration of at least 10 TMS procedures
- 3) Demonstration of inter-rater reliability on motor threshold determination
- 4) Current Basic Life Support certification
- 5) In-service training on basic TMS safety and risks by TMS-trained physician
- 6) In-service training on recognition and initial response to seizures

## **8. Subject Safety Monitoring**

A credentialed physician or nurse practitioner will be on site for all rTMS administration and immediately available. This is the standard of care in community and academic clinical and experimental rTMS centers, nationwide. Study staff will be trained in rTMS administration, rTMS safety, and the measurement of the motor evoked potential threshold and will have performed 10 measurements under supervision. Study staff will monitor individuals during participation and participants will be encouraged to tell experimenters of any discomfort. Any subject exhibiting distress or who wishes to stop the experiment for any reason will be allowed to stop. Participants may withdraw at any time. Data of those participants that have completed at least the first session of any experiment (i.e. both MRI scan and behavioral assessment) will be kept and analyzed. A researcher may end experimentation for the following reasons:

- Abnormal response to rTMS including the occurrence of a seizure, loss of consciousness, or the participant's unwillingness to continue or headache produced by rTMS.
- Withdrawal of consent and/or decision to terminate.
- The experiment will be ended if the participant is unwilling to continue due to pain, or frustration with the procedures

## **9. Outcome Measures**

### **a. Primary outcome measures**

- Pre-to-Post rTMS differences in rsFC and tbFC within the targeted memory network.

### **b. Secondary outcome measures**

- Pre-to-Post rTMS differences in WPT-O scores
- Pre-to-Post rTMS differences in WPT-F scores
- Pre-to-Post rTMS differences in rsFC and tbFC between memory networks.

### **c. Exploratory outcome measures**

- Correlations between network FC changes and:
  - ARSQ scores
  - NIH Toolbox Scores
  - WPT-F scores
  - WPT-O scores

## **10. Statistical Analysis**

### **a. Analysis of data/ study outcomes**

Our primary aim is to examine stimulation-dependent changes in FC within the targeted network in each study. Secondary aims for this protocol will include all behavioral change data from the WPT-F and WPT-O and changes in FC to the non-targeted network, and between networks.

To calculate FC from resting-state scans, the Pearson correlation coefficients ( $r$ ) between time courses of BOLD activity in a seed region (i.e. hippocampus or striatum) will be calculated to determine the FC before and after rTMS stimulation. They will be Fisher-transformed to normalize  $r$ -values.

To calculate FC from task-based scans, the time series from a seed region will be inputted into a general linear model analysis as a regressor along with a regressor indicating when the task is occurring. For the WPT-F, this will include both the choice phase and the feedback phase during learning. For the WPT-O, this will include the observational trials and the retrieval trials. This analysis will be performed on each

individual to create a spatial map of beta values indicating the strength of the association between the seed and other regions during task performance.

*Statistical analysis for Experiments 1 and 3 (targeting the hippocampal network)*

iv. Preliminary Aims

Primary Aim 1

To confirm modulation of the hippocampal network, the average timeseries of the left hippocampal seed will be correlated with all other voxels with available data before and after stimulation. These data will be submitted to AFNI's 3dLME linear mixed effects function, which will be used to reveal potential areas of significant change in rsFC and tbFC.

v. Secondary Aims

Secondary Aims

Behavioral data will be submitted to a 3 x 2 x 2 ANOVA using timepoint (Pre-stimulation, post-stimulation, and follow-up), group (PPC vs. Vertex), and learning type (procedural and declarative) as factors. A significant interaction ( $p < 0.05$ ) between time, group, and learning type will confirm network-dependent modulation of each memory type.

To confirm changes in FC, a similar analysis will be performed as Primary Aim 1, except that the timeseries of the right striatum seed will be used instead of the hippocampal seed.

*Statistical Analysis for Experiments 2 and 4 (targeting the striatal network)*

i. Preliminary Aims

Preliminary Aim 1

To confirm modulation of the striatal network, the average timeseries of the right striatum seed will be correlated with all other voxels with available data before and after stimulation. These data will be submitted to AFNI's 3dLME linear mixed effects function, which will be used to reveal potential areas of significant change in rsFC and tbFC.

ii. Secondary Aims

Secondary Aims

Behavioral data will be submitted to a 3 x 2 x 2 ANOVA using timepoint (Pre-stimulation, post-stimulation, and follow-up), group (M1 vs. Vertex), and learning type (procedural and declarative) as factors. A significant interaction ( $p < 0.05$ ) between time, group, and learning type will confirm network-dependent modulation of each memory type.

To confirm changes in FC, a similar analysis will be performed as Primary Aim 1, except that the timeseries of the left hippocampus seed will be used instead of the striatal seed.

*Interim Analysis for Experiments 3 and 4.* The data from 3 initial participants in Experiments 3 and 4 will be examined to confirm that cTBS is inhibiting our networks of interest. FC will be calculated within the targeted networks and analyzed by study investigators. If, in the opinion of the study team, inhibition of these networks is unreliable, a cohort of 3 subjects will be run and will receive 1-Hz stimulation instead. Following this cohort, the results will be compared between stimulation protocols and the study team will make an informed decision about whether to continue with cTBS or to switch to 1-Hz stimulation instead.

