#### Design

This study contains four between-subjects experiments and is a mixed inter-/intra subject design. Experiment 1 will use nominally excitatory stimulation targeting the hippocampal network to increase FC within the hippocampal network. We also expect to increase FC between the hippocampal and striatal networks, increased declarative memory, and a possible decrease in procedural, learning. Experiment 2 will use excitatory stimulation targeted to the striatal network. We expect this to cause stronger within-network FC in the striatal network, increased FC between the hippocampus and the striatal network and concomitant behavioral effects. Experiments 3 and 4 will be similar except that we will target nominally inhibitory stimulation to these networks and look for the inverse results. FC will be measured under resting and task-activated conditions and active rTMS will be compared to vertex sham.

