#### Outcome measures

The primary outcome measure is the change in FC produced by rTMS within the targeted network. Between-network FC changes and corresponding memory changes will be secondary outcomes. Exploratory measures will include correlations between individual cognitive differences (questionnaires and NIH Toolbox scores), and our primary and secondary outcome measures.

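### Section 10.a writes the primary FC analysis as a whole-brain before/after map and does not specify the active-versus-vertex, within-network test; the sample size rests on a different, uncontrolled single-region effect

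*Combined protocol and SAP*

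**What the plan says.** The Précis defines the outcome: "The primary outcome measure is the change in FC produced by rTMS within the targeted network". Section 9.a repeats it as "Pre-to-Post rTMS differences in rsFC and tbFC within the targeted memory network". The Design paragraph of the Précis says that "active rTMS will be compared to vertex sham", and Table 2 in section 4.a shows an active and a vertex group in each experiment.

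For Experiments 1 and 3, section 10.a says that "the average timeseries of the left hippocampal seed will be correlated with all other voxels with available data before and after stimulation". The results go to AFNI's 3dLME, "which will be used to reveal potential areas of significant change in rsFC and tbFC". For Experiments 2 and 4 the text is parallel: "the average timeseries of the right striatum seed will be correlated with all other voxels with available data before and after stimulation".

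The behavioural secondary outcome in the same section is specified more fully. It has named factors, including group, and a criterion of p < 0.05 for an interaction "between time, group, and learning type will confirm network-dependent modulation of each memory type".

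The primary aims (2.a) join the two FC measures with 'or', while section 9.a joins them with 'and'. Task-based FC comes from two tasks, WPT-F and WPT-O (4.d.iii, Task-Based FC).

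Section 10.b bases the sample size on a repeated-measures ANOVA of one value, FC between the hippocampus and the precuneus/medial occipital cortex. Its inputs are a mean difference of 0.16, a pooled SD of 0.21, d = 0.75, alpha 0.05 and power 0.80, and it arrives at 13 per group. The effect comes from the nine pilot subjects of section 1.b, measured before and after stimulation, with no vertex arm described.

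**The concern.** Three parts of the plan describe three different quantities. The outcome is within-network change, and the design sets it against vertex. The written analysis searches every voxel for change from before to after. The power calculation concerns one seed-to-region value.

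If 10.a is followed as written, a cluster outside the targeted network, or a change common to both arms, could be presented as confirming modulation. The choice of region, and of resting-state FC, WPT-F FC or WPT-O FC, would stay open until the maps had been seen. In Experiments 3 and 4 the investigators also look at FC in the first three actively stimulated subjects, so any region not fixed beforehand could be shaped by that look. The stated 80% power belongs to a test that 10.a does not describe.

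**Working it through.** **1. Reproducing the plan's figure (d = 0.75, alpha 0.05, power 0.80).** Sidedness, number of time points, pre-post correlation and tested term are not stated, so several settings were tried.

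- One-arm paired t test, one-sided: noncentrality 0.75 × √13 = 2.70 on 12 df gives power 0.82. With 12 subjects it is 0.785. So n = 13, an exact match. Two-sided, n = 16.
- RM-ANOVA group-by-time interaction, f = d/2 = 0.375, three time points, correlation 0: λ = f² × N × m/(1 − ρ) = 0.1406 × 26 × 3 = 10.97 on 2 and 48 df gives power 0.83. N = 24 gives 0.79, so N = 26 also matches. With two time points and correlation 0.5, N = 18 would suffice.
- Two-sample t test of change at d = 0.75, two-sided: 29 per group, so no match.

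The 26 therefore reproduces, but only under settings that the plan does not give.

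**2. What the pilot implies (1.b and 10.b).** The standardised change is 2.73/√9 = 0.91, so the SD of change is 0.16/0.91 = 0.176. If 0.21 were the SD of change, t would be 3 × 0.16/0.21 = 2.29 (p = 0.052), not the reported 2.73. If 0.21 is a pooled pre/post SD, the correlation is 1 − 0.176²/(2 × 0.21²) = 0.65.

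**3. Power for active versus vertex, 13 per arm, two-sided 0.05.** Assume an active change of 0.16 and no vertex change. The noncentrality is effect × √(13/2), on 24 df for change scores and 23 df with baseline adjustment.

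| Reading | Standardised effect | Power |
|---|---|---|
| SD of change 0.176 | 0.91 | 61% |
| SD of change 0.21 | 0.76 | 46% |
| Baseline-adjusted, ρ = 0.65 | 0.91 × √(2/1.65) = 1.00 | 69% |
| 0.21 is a single-scan SD, ρ = 0.2 | 0.16/(0.21 × √1.6) = 0.60 | 31% |
| 0.21 is a single-scan SD, ρ = 0.8 | 0.16/(0.21 × √0.4) = 1.20 | 84% |

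The last two rows are for change scores.

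**4. False claims if either FC measure may count.** Assume unadjusted, independent tests.

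- One-sided 0.05 tests, or two-sided tests where either direction counts: 1 − 0.95² = 9.75% for two measures, and 1 − 0.95³ = 14.3% if the two tasks count separately.
- Two-sided 0.05 tests where only the stated direction counts: 1 − 0.975² = 4.9% and 1 − 0.975³ = 7.3%.

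Whole-brain multiplicity comes on top. It cannot be calculated from the documents, which give no threshold or search volume.

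**The case against.** The strongest reply is that the intent is plain. The Précis mentions FC and the vertex comparison in one sentence, section 4.d.iv calls vertex a negative control, and 10.a opens by speaking of stimulation-dependent change in the targeted network. For the interim look, "FC will be calculated within the targeted networks and analyzed by study investigators". Section 10.b adds a model, a region, an alpha level and two groups. 3dLME can carry a group-by-time term. All of this stands. A reader might infer that the plan excludes the vertex comparison or cannot test it; the documents do not support that. The contrast is unspecified, not ruled out.

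A reader might also infer that the 80% power is refuted. It is not. N = 26 reproduces under some settings, and a one-sided, baseline-adjusted test at ρ = 0.65 gives about 80%. The 0.65 is itself back-calculated from nine subjects.

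Nor is 9.75% or 14.3% the unconditional error rate. The aims are directional and sidedness is not stated, so 4.9% or 7.3% is equally open.

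The primary time point is not a serious gap. Section 9.a says pre-to-post, Table 2 labels the two-week visit separately, and section 4.b.i counts a participant as complete without that visit. The 24-hour scan is clearly implied. The lack of striatal pilot data and the uncertainty about cTBS are already disclosed in 10.b and 4.d.iv.

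What the reply does not supply is any sentence in 10.a that turns the intent into a contrast, a region, an error rate or a rule for the FC measures.

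**Conclusion.** The concern stands as a gap in specification together with a mismatch between 10.a and 10.b, and it must be fixed. It affects the primary outcome of all four experiments. It would be wrong to describe the sample size as resting on a vertex-controlled effect: only the 13 + 13 layout is controlled, and the pilot effect is not.

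For the comparison that the design calls for, two-sided power is about 61% on change scores under the SD best supported by the pilot t statistic, 46% if 0.21 is the SD of change, and about 69% with baseline adjustment. The wider range of 31% to 84% reflects how little the documents fix. Every figure assumes no vertex change and a true effect equal to that of the facilitatory parietal pilot. None of them carries over to the striatal experiments, and they say little about inhibitory stimulation.

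**What to change.** In 10.a, make the primary test the active-versus-vertex difference in pre-to-24-hour change, adjusted for baseline FC, in one pre-specified seed-to-mask value per participant.

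- **Regions.** Use the left hippocampal seed with the precuneus/medial occipital mask of 10.b for Experiments 1 and 3, and the right striatal seed with a named mask for Experiments 2 and 4. Fix all masks before any post-rTMS data are seen, including the three-subject looks.
- **FC measure.** Name one primary measure. If it is task-based FC, say which task is used or how WPT-F and WPT-O are combined. Otherwise apply Holm across every measure that can count as success. The choice is the sponsor's, since section 1.c suggests that task-based FC may be the better measure.
- **Whole-brain map.** Keep 3dLME as supportive, with a group-by-time term and cluster-level familywise control.
- **Power.** Restate 10.b for this contrast with its sidedness, time points, correlation and zero-vertex-change assumption, and show the range above. Do not carry the 80% over to the striatal experiments, for which 10.b already reports no preliminary data.

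The cost is that effects outside the mask become supportive, and the stated power becomes less favourable under most assumptions. With Holm over two measures, power for a single responding measure at the first step (0.025, two-sided, ρ = 0.65) is about 57% rather than 69%; the chance of at least one success is higher if both respond. No extra scans or enrolment are needed.
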